8.2.5. Safety Analyses

The safety assessments in the study are listed in [Section 6.2](#). All randomized subjects who receive at least one dose of study treatment will be included in the safety analysis. All adverse events that are observed from the time of first dosing with study medication (at randomization) until the end of study participation will be included in the safety analysis.

All adverse events will be coded according to the Medical Dictionary for Regulatory Activities (MedDRA) and will be summarized by treatment group. The incidence of treatment-emergent adverse events will be tabulated by treatment group and by system organ

class. The incidence of treatment-emergent adverse events will be displayed by severity and attribution. In addition, the incidence of serious adverse events and adverse events that cause withdrawal will be tabulated. All adverse events will be listed.

The effective duration of treatment is determined by the lag time. Any event occurring within the lag time, whether this occurs during a break in treatment or at the end of treatment, is attributed to the corresponding treatment period. A lag of 28 days will be used for this study.

The following 3-tier approach will be used to summarize AEs. Under this approach, AEs are classified into 1 of 3 tiers. While the AEs will be additionally analyzed by subgroups, the 3-tier approach will only be applied to the overall AE analyses.

Tier-1 events: These are pre-specified events of clinical importance and are maintained in a list in the product's Safety Review Plan. This list may be updated as more is understood about the drug.

Tier-2 events: These are events that are not tier-1 but are "common". A MedDRA Preferred Term (PT) is defined as a tier-2 event if there are at least 4 in any treatment group.

Tier-3 events: These are events that are neither tier-1 nor tier-2 events.

The analyses of adverse events under the 3-tier approach is considered exploratory. There will be no adjustment for multiple comparisons or stratification factors in the analyses. For tier-1 and tier-2 events, the proportion of AEs observed in each treatment groups will be presented along with the point estimates and associated 95% confidence intervals of the risk difference for the pooled tafamidis group compared with placebo.

For Tier-1 events p-values will be included in the presentations. AEs will be arranged in the output sorted in descending point estimate of the risk difference within system organ class. Footnotes in the outputs will include the methods used to derive any p-values and confidence intervals as per Pfizer standards. The Tier 1 AEs will be analyzed using the approach of [Chan and Zhang \(1999\)](#) who inverted two one-sided tests at half the significance level each for calculating P-values and confidence intervals.

For Tier 2 AEs, both proportion and 95% CIs will be generated using an asymptotic approach (Proc Binomial). A MedDRA PT is defined as a Tier-2 event if there are at least 4 in any treatment group. A cross-industry expert team on safety planning, evaluation and reporting ([Crowe et al, 2009](#)) suggests to use the "Rule of 4" to define tier-2 events. The "Rule of 4" says that if a trial has 400 or fewer subjects per group and there are 4 or more subjects with a given MedDRA PT in any treatment group, then that PT will be categorized as a tier-2 event.

For Tier 3 events, simple proportions will be presented.

All clinical laboratory data will be subjected to clinical review, summarized by frequency of events and mean changes from baseline.

All vital sign measurements will be displayed in listings by subject for each sample collection date and time. The measurement taken immediately prior to randomization will be used as the baseline for calculating changes in vital signs.

Centrally over-read ECG variables will be summarized by mean change from baseline to each measurement time for heart rate, PR interval, QRS width, QT interval and QTcB (Bazett’s correction) and QTcF (Fridericia correction) values. Additionally, the incidence of categorical increases in QTc intervals will be provided. Categories for QTcF and QTcB are ≥ 450 msec, ≥ 480 msec, and ≥ 500 msec. Categories for QTcF and QTcB as change from baseline are ≥ 30 msec increase, ≥ 60 msec increase and ≥ 75 msec increase. QTcF is considered the primary QTc value as this correction is more appropriate.

All of the analysis on the safety endpoints will compare placebo with each tafamidis dose (20 mg and 80 mg) as well as the pooled group (combined tafamidis 20 mg and 80 mg).

The safety analyses will also be summarized by TTR genotype and NYHA baseline classification. Treatment-emergent adverse events and serious adverse events will be summarized by gender as well.

Summary of Efficacy Analyses

Table 2. Summary of Proposed Efficacy and Safety Analyses

End Point or Assessment	Overall	By dose	Wild-type vs Variant	NYHA Baseline Classification
Primary Analysis				
Primary – FS Method (All-cause mortality and CV Hospitalization)*	X [#]	x	x	x
Key-Secondary Analyses				
Change from Baseline to Month 30 on the distance walked during 6-Minute Walk Test (6MWT)*	X ^{##}	x	x	x
Change from Baseline to Month 30 on the Kansas City Cardiomyopathy Questionnaire Overall Score (KCCQ-OS)*	X ^{##}	x	x	x
Secondary Analyses				
Cardiovascular-related mortality	x	x	x	x
Frequency of cardiovascular-related hospitalization	x	x	x	x
All-cause mortality	x	x	x	x
TTR stabilization at Month 1	x	x	x	-
Exploratory Analyses				
TTR stabilization at each time point other than month 1	x	-	-	-
Frequency of all-cause hospitalization	x	-	-	-
Cardiovascular-related Days Hospitalized	x	-	-	-
All-cause Days Hospitalized	x	-	-	-
FS-method – All-cause mortality and frequency of all-cause hospitalization	x	-	-	-
FS-method – all cause mortality + CV-related hosp days	x	-	-	-
FS-method – CV-related mortality + frequency of CV-related hosp	x	-	-	-

End Point or Assessment	Overall	By dose	Wild-type vs Variant	NYHA Baseline Classification
Change from Baseline at each time point on EuroQoL-5Dimensions (EQ-5D-3L) Index Score and visual analog scale (VAS) scores	x	-	-	-
TTR oligomer concentration at each time point	x	x		
TTR concentration at each time point	x	x		
Patient Global Assessment at each time point	x	-	-	-
NYHA classification change from baseline (shift table)	x	-	-	-
Change from Baseline at each time point on Kansas City Cardiomyopathy Questionnaire: (KCCQ) domain scores (Physical limitation, Symptom stability, Symptom frequency, Symptom burden, Total symptom, Self-efficacy, Social limitation, and Quality of life) and clinical summary scores	x	-	-	-
Change from Baseline at each time point on Modified BMI Mass Index	x	-	-	-
Change from Baseline at each time point in Echocardiography (septal and ventricular wall thickness, ejection fraction, and stroke volume, Global longitudinal strain, Circumferential strain mid global, Radial strain mid global)	x	-	-	-
Change from Baseline at each time point on NT-proBNP concentration	x	-	-	-
Change from Baseline at time points other than month 30 on the distance walked during 6-Minute Walk Test (6MWT)	x	-	-	-
Change from Baseline at time points other than month 30 on the Kansas City Cardiomyopathy Questionnaire Overall Score (KCCQ-OS)	x	-	-	-
Additional echocardiographic parameters (listed in Section 6.1.4)	x			
Safety				
AEs labs, Vitals	X	X	X	X

*Analysis will be performed using both ITT and PP Analysis Sets. All other efficacy analysis will be performed on ITT Analysis Set only.

#Sensitivity analysis of the primary analysis will be done as described in [Section 8.2.4](#).

Supplemental analysis of the key-secondary endpoints will be done as described in [Section 8.2.2](#).

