9.1. Sample Size Determination

The primary comparison of interest is the pooled tafamidis 20 mg and 80 mg treatment groups vs. placebo. The target sample size is 400 subjects.

A sample size of 400 subjects is based on findings from study Fx1B-201 (a 12-month, open-label study of tafamidis in TTR-CM subjects), TRACS (an observational study with no treatment intervention other than standard of care in TTR-CM subjects), an understanding of current clinical outcomes in this population, and the uncertainty of the assumptions derived from these limited data.

Given that no closed-form sample size estimation solution is available for the primary analysis method, sample size estimation was performed based on simulations.

Sample size assumptions include:

1. All-cause mortality rate of 12.5% for the tafamidis group and 25.0% for the placebo group (ie, a 50% reduction in mortality with treatment).
2. 1.5 cardiovascular-related hospitalizations for the tafamidis group and 2.5 cardiovascular-related hospitalizations for the placebo group.
3. Treatment duration of 30 months.
4. Significance level (alpha) of 0.05 (two-sided test).

With these assumptions, 300 subjects (n=120 for placebo, n=60 for 20 mg, n=120 for 80 mg) yields a power of over 90% for the primary comparison. A more conservative assumption of 30% reduction in mortality (17.5 % for tafamidis and 25% for placebo) yields a power of approximately 80%. With an assumption of 30% reduction in mortality and increasing the number of subjects to 400 subjects (n=160 for placebo, n=80 for 20 mg, and n=160 for 80 mg) yields a power of approximately 90%.

Summary of operating characteristics:

| Assumptions | Sample Size | Power |
|--|--------------------|--------------|
| 50% mortality reduction, hosp frequency 2.5 (pbo), 1.5 (taf) | N=300 | 96% |
| 30% mortality reduction, hosp frequency 2.5 (pbo), 1.5 (taf) | N=300 | 80% |
| 30% mortality reduction, hosp frequency 2.5 (pbo), 1.5 (taf) | N=400 | 90% |

pbo=placebo, taf=tafamidis

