Appendix 1.3. Sample SAS Code for Analyses Described in Sections 8.1.2 – 8.2.6

Sample SAS code to fit the mixed model repeated measures specified in [Section 8.1.3](#) is given below. The response variable Y is the change from baseline at the study visits.

```
PROC MIXED DATA=xxx METHOD=REML EMPIRICAL;  
CLASS pid center trt visit genotype;  
MODEL y= ybase trt visit genotype trt *visit;  
RANDOM int/SUBJECT=center;  
  
REPEATED visit /SUBJECT= pid (center) r type=UN;  
  
RUN;
```

Sample SAS code for the survival analysis specified in [Section 8.1.2](#) is given below.

```
PROC LIFETEST DATA=xxx PLOTS=(s) graphics;  
TIME dur *status(0);  
STRATA trt;  
RUN;  
  
PROC PHREG DATA=xxx;  
MODEL dur*status(0)=trt genotype NYHAbase/ ties=EXACT;  
RUN
```

Sample SAS code for the ANOVA specified in [Section 8.1.4](#) is given below.

```
PROC GLM DATA=xxx;  
CLASS trt genotype NYHAbase;  
MODEL y= trt genotype NYHAbase trt*genotype trt*NYHAbase;  
RUN;
```

Sample SAS code for the Poisson regression specified in [Section 8.1.5](#) is given below.

```
PROC DATA=xxx;  
ln_styyr=log(styyr);* log transformation to normalize duration of participation ;  
RUN;  
  
PROC GENMOD DATA=xxx;  
CLASS trt genotype NYHAbase;  
MODEL y= trt genotype NYHAbase trt*genotype  
trt*NYHAbase/ type 3 dist=poisson link=log offset=ln_styyr;  
RUN;
```

Sample SAS code for the CMH test specified in [Section 8.1.6](#) is given below. In the code below, the variable NYHA_GENOTYPE is obtained from combining NYHA baseline classification and TTR genotype into one variable (with 4 levels).

```
PROC FREQ DATA=xx;
TABLES NYHA_GENOTYPE*TRT*STABILIZED / CMH
RUN;
```

Sample SAS code for the pattern mixture analysis specified in [Section 8.1.5](#) is given below.

```
PROC MIXED DATA=xxx empirical;
CLASS pid visit center trt pattern genotype;
MODEL y= ybase visit trt genotype pattern visit*trt
trt*pattern / solution;
random int/subject=center;
repeated visit /subject= pid (center) r type=UN;
ESTIMATE 'Tafamidis vs placebo Month 30'
trt 1 -1 visit*trt 0 0 0 0 0 0 0 1 -1
trt*pattern 0.5 0.5 -0.5 -0.5 /cl e; * Placebo adjusted LSMEANS of Tafamidis
averaged over the pattern (equal weight=0.5);
run;
```

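### SAP 8.2.5 compares adverse events only as crude proportions; adding rates per patient-year would cheaply remove a modest distortion from unequal time at risk (about 4-8% relative for events unrelated to drug or disease)

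*SAP*

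**What the plan says.** SAP 8.2.5 includes adverse events from first dose to the end of the subject's participation. For tier-1 and tier-2 events, "the proportion of AEs observed in each treatment groups will be presented along with the point estimates" and 95% intervals of the risk difference, pooled tafamidis against placebo. Tier-1 events also get p-values, and tier-3 events get simple proportions. The output is sorted by the size of the risk difference within system organ class. Treatment emergence is settled by a lag: "A lag of 28 days will be used for this study". The section calls the tiered analysis exploratory and rules out adjustment for multiplicity or stratification factors; it does not mention exposure. Protocol 9.5 likewise tabulates incidence.

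Protocol 9.1 powers the trial on "All-cause mortality rate of 12.5% for the tafamidis group and 25.0% for the placebo group", and then on "A more conservative assumption of 30% reduction in mortality (17.5 % for tafamidis and 25% for placebo"). The second assumption is the one paired with 400 subjects in the operating-characteristics table.

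Hospitalisation counts are treated differently. SAP 8.1.5 adjusts them for treatment duration, and the sample code in SAP Appendix 1.3 does so with "dist=poisson link=log offset=ln_styyr".

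**The concern.** A subject who has died, withdrawn or been discontinued contributes no further adverse events. If one arm is observed for longer, it collects more background events at the same underlying rate, and a crude risk difference cannot separate event rate from length of observation. Under the plan's own assumptions the longer-observed arm is tafamidis, so a real survival benefit would create a small apparent excess of unrelated events on the drug and move those terms up the sorted tables. If instead a dose led to more early stopping, its time at risk would shrink and a true harm could be understated. The 28-day lag decides which events count; it does not equalise time between arms. The SAP already recognises the issue for hospitalisations and gives no reason for leaving adverse events unadjusted.

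**Working it through.** **The plan's own figures.** Neither document states an adverse-event rate or an exposure figure, so there is none to reproduce directly. The mortality inputs are taken as 30-month risks. That reading is consistent with the stated power of 96%, 80% and 90%: simulating the Finkelstein-Schoenfeld test of SAP 8.1.1 with exponential death and gamma-Poisson hospitalisation counts (dispersion 1.2, which is an assumption) gave 96.2%, 81.4% and 90.6%. Plain Poisson counts gave 99.9%, 99.7% and 100%, so the agreement depends on the dispersion chosen.

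**Inputs.** Mortality 25% on placebo and 12.5% or 17.5% on tafamidis, over 30 months (Protocol 9.1). Subjects: 160 placebo and 80 + 160 = 240 pooled tafamidis (Protocol 3). Assumed: constant hazards and, at first, no dropout other than death.

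**Step 1, time at risk.** Death hazard m = -ln(1-p)/30; mean time observed = p/m.

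| Mortality p | m per month | Mean months | Ratio to placebo |
|---|---|---|---|
| 25% (placebo) | 0.009589 | 26.07 | - |
| 12.5% | 0.004451 | 28.08 | 1.077 |
| 17.5% | 0.006412 | 27.29 | 1.047 |

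**Step 2, crude proportion of an unrelated event.** The event hazard is the same in both arms, l = -ln(1-r)/30, where r is the 30-month risk if nobody died. The crude proportion is l/(l+m) × (1 - exp(-30(l+m))). For r = 20%, l = 0.007438; for r = 40%, l = 0.017028.

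| r | Placebo | Tafamidis at 12.5% | Tafamidis at 17.5% |
|---|---|---|---|
| 20% | 17.47% | 18.77% (+1.3 points, ratio 1.074) | 18.26% (+0.8, 1.045) |
| 40% | 35.18% | 37.66% (+2.5, 1.070) | 36.68% (+1.5, 1.043) |

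The ratio approaches the exposure ratio, 1.077 or 1.047, only for rare events. This gives the range of about 4-8%.

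**Step 3, against the planned precision.** Half-width = 1.96 × sqrt(p1(1-p1)/160 + p2(1-p2)/240). For r = 20% at 12.5% mortality: 1.96 × sqrt(0.1747 × 0.8253/160 + 0.1877 × 0.8123/240) = 7.7 points. For r = 40% it is 9.6 points. The shifts are 17% and 26% of these half-widths, or 10% and 16% under the 17.5% assumption. By normal approximation, the chance that the interval for an unrelated event lies wholly above zero rises from 2.5% to about 4% (r = 10%) and 9% (r = 50%) at 12.5% mortality.

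**Step 4, timing of the event.** At 12.5% mortality the ratio is about 1.01 for an event confined to the first 3 months and about 1.13 for one confined to the last 12.

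**Step 5, discontinuation.** No dropout rate is stated, so 10% and 20% extra discontinuation in the tafamidis arm alone are assumptions. Adding a hazard of -ln(1-d)/30 to m at 12.5% mortality lowers 18.8% to 17.9% (d = 10%) or 16.9% (d = 20%), against 17.5% on placebo. At 20% the sign has reversed.

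**Step 6, what a rate does.** For r = 20%, mean time to first event, death or month 30 is (1 - exp(-30(l+m)))/(l+m) = 23.49 months on placebo and 25.23 on tafamidis at 12.5%. First events per 100 patient-years are 0.1747/23.49 × 1200 = 8.93 and 0.1877/25.23 × 1200 = 8.93. The artefact disappears.

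**The case against.** The strongest reply is that a crude proportion is a legitimate measure. If death is the only reason observation ends, it correctly estimates the probability of experiencing the event within 30 months, and living long enough to have one is a real consequence of treatment. Rates answer a different question and need a roughly constant hazard. This stands, and it is why the rates should sit beside the proportions and not replace them.

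It is also fair that the shift is small against the planned precision, that the tiered analysis is exploratory with no decision rule attached, and that the gravest outcomes already have time-based analyses: survival methods for mortality (SAP 8.1.2) and a duration offset for all-cause hospitalisation (SAP 8.1.5). That cover does not reach individual preferred terms or events managed outside hospital.

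A reader might infer that heart-failure events would also show a spurious excess on tafamidis. The documents do not support this. Protocol 9.1 assumes "1.5 cardiovascular-related hospitalizations for the tafamidis group and 2.5 cardiovascular-related hospitalizations for the placebo group", a reduction of (2.5 - 1.5)/2.5 = 40%. If heart-failure events fell by the same proportion, the Step 2 formula at 12.5% mortality gives 17.5% on placebo against 11.7% on tafamidis for a 20% event, and 35.2% against 24.8% for a 40% event: a clear deficit.

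**Conclusion.** The omission is real and its direction is predictable, but its size is modest. Under the plan's two mortality assumptions, an event unrelated to drug or disease would appear about 4-8% more often, in relative terms, on tafamidis: +0.8 to +1.3 points for a 20% event and +1.5 to +2.5 points for a 40% event. This requires that the assumed survival benefit is real, that the event hazard is roughly constant and that other dropout is balanced. Unequal discontinuation could reduce or reverse the shift, by an amount that cannot be derived from the documents.

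A reader might take 8% as the general figure; it is the exposure ratio under the more optimistic mortality assumption, and the assumption paired with 400 subjects gives 4-5%. A reader might also conclude that the safety comparison is invalid, or that the data monitoring committee's summaries must change. The first is not borne out by shifts of 10-26% of a confidence-interval half-width. The second would rest on a charter that is not among the documents; SAP 3 already lets the committee request further safety data. The point is a cheap improvement.

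**What to change.** In SAP 8.2.5, keep the crude proportions and risk differences. Add, for tier-1 and tier-2 events, serious adverse events and adverse events leading to withdrawal, the number of subjects with a first event per 100 patient-years at risk. Time at risk runs from first dose to the earliest of first event, death, 28 days after last dose, or end of participation. Give the rate difference versus placebo with a 95% confidence interval.

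The cost is SAP wording and extra table columns, derived from dates already collected; trial conduct and the primary analysis are untouched. The downsides are longer tables and a summary that is easiest to read when the hazard is roughly constant, which should be footnoted.

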In the elderly, wild-type (normal) TTR may become structurally unstable and result in deposition of amyloid fibrils, primarily in heart tissue, and may lead to diastolic dysfunction, restrictive cardiomyopathy and heart failure (Pages 1973, Saraiva 2001, Hammarström 2002, Quintas 2001).^{45,25,38} The frequency of TTR amyloid deposition in cardiac ventricles reported from autopsy studies in subjects >80 years of age range from 1.8% (Jacobson 1997)²⁹ to 16.5% (Cornwell 1983)¹⁰, with a rate of clinical cardiac disease premortem of 34% (Cornwell 1983).¹⁰

TTR-CM is a late onset disease with symptoms typically occurring in subjects aged 60 years or older, though the L111M variant may express TTR-CM in subjects at an earlier age.

Symptoms of TTR-CM are not mutation-type dependent and are typical of restrictive cardiac disease, and include dyspnea on exertion, orthostatic hypotension, and syncope, as well as conduction abnormalities, including bundle branch block, atrioventricular block, sinoatrial block, and atrial fibrillation. Objective measures of cardiac involvement include abnormal electrocardiogram (ECG) with findings including low voltage, left and right ventricular wall thickening by echocardiogram, and elevated cardiac biomarkers (Connors 2009).⁸ These findings are non-specific for heart failure, making the diagnosis of cardiac amyloidosis difficult and resulting in likely under diagnosis of this condition (Falk 2011).¹⁵

Median survival from diagnosis for patients with TTR-CM was 41 months in a study of the V122I mutation and median survival was reported as 46 months for wild-type (Connors 2011).⁹ Death in most patients with cardiac amyloidosis is from cardiac causes, including sudden death, heart failure, and myocardial infarction (Kyle 1996, Smith 1984).^{31,47}

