Except for symptom management, such as use of diuretics for symptoms of heart failure and pacemaker placement for cardiac arrhythmias, the only treatment option currently available for TTR-CM patients is orthotopic liver transplant. This may be combined with heart transplant, depending on organ availability, patient capacity to tolerate the combined transplant, and the severity of cardiac amyloidosis at the time of transplant. Transplantation of the liver removes the primary production site of amyloidogenic mutant TTR protein and replaces it with the production of wild-type TTR (Lewis 1994, Holmgren 1993).^{33,27} The Familial Amyloidotic Polyneuropathy World Transplant Registry (FAPWTR) includes data on combined heart and liver transplant that indicates that this procedure is relatively infrequent, documenting 6 cases out of 575 transplantations (Herlenius 2004).²⁶ The mean age of those undergoing combined heart and liver transplant was older (58±5 years) than those undergoing liver transplant alone (40±11 years, p<0.001).

Tafamidis is an oral small molecule, under development by Pfizer, as a disease modifying therapy for TTR amyloid diseases. It binds to the thyroxine binding sites on the TTR tetramer, thereby preventing destabilization into the monomeric form. It has been demonstrated to bind selectively to TTR in human blood and slow fibril formation in vitro (Razavi 2003).⁴⁰ It binds to the 2 thyroxine binding sites with negative cooperativity, exhibiting dissociation constants of 2 nM [K_{d1}] and 154 nM [K_{d2}] (DeVit 2006)¹¹ and kinetically stabilizing the TTR tetramer when bound (Sekijima 2009).⁴⁶

TTR stabilization has been hypothesized to lead to slowing or halting of disease progression. This hypothesis was confirmed in study Fx-005, a double-blind, placebo-controlled, 18-month study in subjects with TTR-FAP, in which those subjects receiving tafamidis had better neurologic outcomes compared with those receiving placebo. In order to improve the understanding of the natural history of TTR-CM, a longitudinal, observational clinical study of 29 subjects with either the V122I genetic variant (11 subjects) or wild-type (18 subjects) associated TTR-CM (Transthyretin Amyloid Cardiac Study; TRACS) was undertaken. A follow-up Phase 2 open-label interventional study (Study Fx1B-201) demonstrated TTR

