Non-invasive cardiac assessments demonstrated significant cardiac involvement at Baseline in study Fx1B-201, with substantial ventricular wall thickening on echocardiography and cardiac magnetic resonance imaging (MRI) and elevated intra-cardiac filling pressures on echocardiography. There were no consistent clinically relevant changes in the echocardiography parameters over time. For the wild-type subjects, who were the majority of subjects in the study, the deterioration in ejection fraction (-4.4%) and stroke volume (-1.9 mL) observed in the Fx1B-201 study was less than that observed in TRACS (-11.3% and -9.0 mL, respectively) at 12 months. Similar findings were observed in a subset of subjects that underwent cardiac MRI. In these subjects in the Fx1B-201 study, there was a decrease in the percent of left ventricle (LV) mass with amyloid observed at 12 months, while there was an increase in LV mass with amyloid observed in TRACS.

Baseline electrocardiogram and 24-hour Holter monitoring demonstrated substantial conduction and rhythm abnormalities, including bundle branch blocks and atrial fibrillation/flutter. There were no clinically relevant changes over time in these assessments, with perhaps slight improvement in cardiac autonomic function in study Fx1B-201 as demonstrated by improved heart rate variability indices.

Over the 12 months of tafamidis treatment in study Fx1B-201, quality of life and functional status was maintained, as assessed by the Short Form-36, patient reported health survey (SF-36), the Kansas City Cardiomyopathy Questionnaire (KCCQ), ([Appendix 1.1](#)) and the Patient Global Assessment (PGA) ([Appendix 3](#)). The majority of these results were also better when compared with TRACS.

Seven subjects participated in both TRACS (median follow-up 12.5 months, with range of 6-26 months) and Protocol Fx1B-201. All seven subjects completed 12 months of treatment with tafamidis. However, given the small number of subjects, it is difficult to assess whether disease progression was different during treatment with tafamidis as compared to standard of care in TRACS. The rate of cardiovascular-related hospitalization was similar between the two 12-month periods, with some evidence of stabilized cardiac function (ejection fraction and fractional shortening) observed following treatment with tafamidis.

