Centrally over-read ECG variables will be summarized by mean change from Baseline to each measurement time for heart rate, PR interval, QRS width, QT interval, and QTcB (Bazett's correction) and QTcF (Fridericia's correction) values. Additionally, the incidence of categorical increases in QTc intervals will be provided. Categories for QTcB and QTcF are ≥ 450 msec, ≥ 480 msec, and ≥ 500 msec. Categories for QTcB and QTcF as change from Baseline are: ≥ 30 msec increase, ≥ 60 msec increase, and ≥ 75 msec increase. QTcF is considered the primary QTc value as this correction is anticipated to be more appropriate.

All of the analysis on the safety endpoints will compare placebo with each tafamidis dose (20 mg and 80 mg) as well as the pooled group (combined tafamidis 20 mg and 80 mg).

The safety analyses will also be summarized by TTR genotype and NYHA Baseline classification.

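### The QTc categories make no allowance for wide QRS or pacing, so their counts mix conduction delay with repolarisation

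*SAP*

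**What the plan says.** SAP section 8.2.5 sets the absolute categories: "Categories for QTcF and QTcB are ≥ 450 msec, ≥ 480 msec, and ≥ 500 msec". It sets the change categories next: "Categories for QTcF and QTcB as change from baseline are ≥ 30 msec increase, ≥ 60 msec increase and ≥ 75 msec increase". Protocol section 9.5 has the same limits and adds "QTcF is considered the primary QTc value as this correction is anticipated to be more appropriate". Fridericia's formula corrects for heart rate; neither document says anything about QRS duration.

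The same SAP section also summarises other intervals: "Centrally over-read ECG variables will be summarized by mean change from baseline to each measurement time for heart rate, PR interval, QRS width", followed by QT, QTcB and QTcF. Safety endpoints are compared with placebo for each dose and for the pooled doses. Safety summaries are repeated by genotype and NYHA class, and adverse events also by gender. There is no flag, exclusion, QRS-adjusted interval or subgroup for wide QRS or pacing.

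On the population, Protocol section 1.2 lists "conduction abnormalities, including bundle branch block, atrioventricular block, sinoatrial block, and atrial fibrillation" among typical features and names "pacemaker placement for cardiac arrhythmias" as part of symptom management. Protocol section 1.2.1 reports that baseline ECG and Holter recordings in the Phase 2 study "demonstrated substantial conduction and rhythm abnormalities, including bundle branch blocks and atrial fibrillation/flutter". Exclusion criterion 18 in Protocol section 4.2 bars subjects with nodal dysfunction only where an indicated pacemaker will not be placed, so a subject who already has one may enroll.

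**The concern.** QT runs from the start of QRS, so a wider QRS lengthens QTc with no change in repolarisation. In a population where bundle branch block is expected and pacing is allowed, a count of subjects above 450, 480 or 500 msec cannot be read as a count of repolarisation abnormalities.

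Change from baseline removes a block that was already there and stays stable. It does not remove block or pacing that begins during the 30 months. Such a subject moves into an increase category because of conduction disease or a device.

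Randomisation balances conduction disease at baseline, not what develops later. The study rationale is that the drug slows disease progression. If that extended to conduction disease, the arms could differ in QTc without any repolarisation effect. That is a possibility, not something the documents show. At stake is how the ECG safety tables are read, including 80 mg against placebo. The primary and key secondary analyses are not touched.

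**Working it through.** The plan states no expected rate, power or precision for QTc, so there is no figure to reproduce. The QTc distribution, the share of wide QRS and the shift it causes are also absent. Everything below except the category limits, the arm size of 160 (placebo and 80 mg, Protocol section 3), the two-sided 0.05 level and the concentrations is assumed, and no QTc test is actually planned.

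**1. Who fills the top category.** Assume narrow-QRS QTcF is Normal with mean 420–430 and SD 25 msec, wide QRS or pacing adds 40–60 msec, and 20–40% of subjects have it. P(QTcF ≥ 500) = 1 − Φ((500 − mean)/25).
- Narrow: (500 − 420)/25 = 3.2 gives 0.07%; (500 − 430)/25 = 2.8 gives 0.26%.
- Wide: (500 − 460)/25 = 1.6 gives 5.5%; (500 − 490)/25 = 0.4 gives 34%.
- Wide share of all cases = w·b/(w·b + (1 − w)·a), where w is the wide fraction and b and a are the wide and narrow rates. Lowest (mean 430, +40, 20%): 0.2 × 0.115/(0.2 × 0.115 + 0.8 × 0.00256) = 92%. Highest (mean 420, +60, 40%): 99.5%.

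**2. New block or pacing.** Assume the SD of change is 20 msec.
- With no QRS change, P(increase ≥ 30) = 1 − Φ(1.5) = 6.7% and P(increase ≥ 60) = 1 − Φ(3) = 0.13%.
- With a new shift of 40–60 msec these become 69–93% and 16–50%.
- If 5–10% of subjects acquire such a shift, they supply 86–98% of all increases of 60 msec or more. At the low end: 0.05 × 0.159/(0.05 × 0.159 + 0.95 × 0.00135) = 86%.

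**3. Can the arms still be told apart?** Take 160 versus 160, a true 10 msec effect, narrow mean 425, SD 25, and the same wide-QRS share in both arms. Power = Φ((|p1 − p0| − 1.96·se0)/se1), with pooled se0 and unpooled se1. With no wide QRS, at 450 msec, p0 = 1 − Φ(1.0) = 0.159 and p1 = 1 − Φ(0.6) = 0.274. Then se0 = 0.0460, se1 = 0.0456 and power is 0.71.

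| Category | No wide QRS | 20–40% wide, +40 to +60 msec |
|---|---|---|
| ≥ 450 | 0.71 | 0.34–0.60 |
| ≥ 480 | 0.24 | 0.22–0.43 |
| ≥ 500 | 0.08 | 0.17–0.34 |

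With a shift of only 30 msec and 20–50% wide, power at 450 msec is 0.65–0.66.

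**4. Change from baseline.** Suppose 20% in both arms acquire a 50 msec shift.
- The SD of change becomes √(20² + 0.2 × 0.8 × 50²) = 28.3, or √(30² + 400) = 36.1 if it was 30.
- Power for the mean = Φ(10/(SD·√(2/160)) − 1.96). It falls from 0.99 to 0.89 (SD 20) and from 0.85 to 0.70 (SD 30).
- For an increase of 30 msec or more, power falls from 0.74 to 0.46 (SD 20) and from 0.55 to 0.43 (SD 30).

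**5. Share of QTc that is QRS.** On assumed values, 95/425 = 22% in a narrow-QRS ECG, and 140/470 = 30% to 160/490 = 33% in a wide one.

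**6. Dropping wide-QRS subjects instead.** At 450 msec, setting aside 20% (128 per arm) gives power 0.61 and setting aside 50% (80 per arm) gives 0.43. Keeping everyone gives 0.53 and 0.41 at +50 msec, and 0.66 and 0.66 at +30 msec. Restriction gains little or loses power; what it buys is a count that can be interpreted.

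**The case against.** A reader might infer that QTc here largely measures QRS width, that pacing is common, and that a drug effect on repolarisation would be buried. The documents do not support any of the three. On the assumed values QRS is about a third of a wide-QRS QTc, and narrow-QRS subjects are unaffected. No rate of bundle branch block or pacing is given anywhere. Step 3 shows power rising at 500 msec, and step 4 shows mean change keeping most of its power.

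The plan has partial safeguards, and they stand. QRS width and PR are summarised separately, so a between-arm shift in mean QRS would be visible. Every safety endpoint has a placebo comparison. ECGs start at Month 1, before much new block or pacing can accrue. The Phase 2 study saw no clinically relevant ECG or Holter changes over time and no apparent adverse effect on conduction or repolarisation, though uncontrolled, in 35 subjects at 20 mg over 12 months.

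The moxifloxacin-controlled QTc study also lowers the stakes. It targeted about 20 µg/mL, against 8.0 µg/mL expected at 80 mg (20/8.0 = 2.5 times), and found no QTc effect. It was a single dose in healthy volunteers, so it does not settle 30 months of dosing in diseased hearts.

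The absence of a rule is read from the protocol and SAP; the separate ECG procedure manual was not available. What survives is narrower: mean QRS does not show which subjects crossed a QTc limit because of QRS, and change from baseline does not remove new block or pacing.

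**Conclusion.** The gap is real and modest. Neither document separates conduction delay from repolarisation in the QTc categories, although the protocol describes a population in which the two will mix. If wide QRS adds 40–60 msec in 20–40% of subjects, almost all values of 500 msec or more come from wide-QRS subjects, and the 450 msec category loses between about a sixth and a half of its power for a 10 msec effect (0.71 to 0.60 or 0.34). The 30 msec increase category is diluted too if new block or pacing occurs. The 480 and 500 msec categories start from low power and mostly do not lose it, and mean change holds up well.

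These sizes rest wholly on assumed distributions, equal wide-QRS shares in the arms and one ECG per subject. The conclusion that the counts are mixed does not depend on them. This is a cheap improvement to safety reporting, not a flaw in the efficacy analysis.

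**What to change.** Keep the all-ECG analysis as the main table in SAP section 8.2.5 and Protocol section 9.5. Before unblinding, add:

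1. A QRS-adjusted summary, JTc = QTcF minus QRS, as mean change by arm for non-paced ECGs. Give the number of ECGs left out as paced, by arm and visit, because pacing that starts on study is itself a post-randomisation event.
2. The QTcF categories split by baseline status: QRS below 120 msec and not paced, versus QRS of 120 msec or more or paced.
3. A flag for ECGs that become wide-QRS or paced on study, shown in a supportive table only.

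Do not make a table restricted to narrow QRS at both baseline and the visit the primary one. That conditions on a post-randomisation variable, and if treatment affected conduction disease it would select subjects differently by arm.

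The cost is SAP wording and a few tables. Protocol section 7.6.4 already collects QRS, an overall interpretation and abnormal findings, with central review. The downsides are smaller numbers in the split tables and the need to confirm that the central over-read identifies paced rhythm, which the documents do not state.
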